### Chinese Herbal Medicine (CHM)

Herbal medicines have been used for millennia in China, during which time several generations of practitioners have described systems of medicine to understand the pathophysiology of viral illness and suggest tools for treatment. The most revered of these works was compiled by Zhang Zhongjing sometime before 220 AD and is known as the “Shang Han Lun,” known in English as the “Treatise on Cold Damage Disease.” This remains one of the foundational texts in modern CHM, and informs the main formulas that are currently being used in combination with Western medicine for the treatment of COVID-19 in China. Unlike the United States, use of CHM is widely used along with Western medicine in the treatment of COVID-19.

CHM is largely well tolerated and adverse events (AEs) in trials tend to be mild when reported. In a narrative review, Jiang concluded CHM can be used in many conditions with minimum side effects (Jiang, 2005). In a cohort of 1,063 people who took CHM to prevent SARS infection, there were no serious adverse events (SAEs). Nineteen (1.8%) reported minor AEs of diarrhea, dizziness, and nausea, and nine participants stopped taking the formula altogether (Lau et al., 2005). Duan et al.’s RCT of patients with H1N1 reported 4 minor AEs in the CHM group. Another trial investigating Oseltamivir and CHM for H1N1 influenza reported two events of nausea and vomiting with CHM alone, but none in the group that combine CHM and oseltamivir (Wang et al., 2011). In a meta-analysis of 12 CHM and SARS trials, only two trials reported AEs. There were no serious adverse events (SAEs) or AEs in the CHM groups (Liu, Zhang, He, & Li, 2012). More details on the specific safety profiles are disclosed in the following section (Study Rationale/Risk / Benefit Assessment).

CHM constitutes common therapy and is used alongside conventional medicine in some Chinese and Taiwanese hospitals (M. C. Chen, Lai, Chen, & Wang, 2013; Ni, Zhou, Zhou, Zhao, & Wang, 2020). Yang et al reported 85% of SARS-CoV-2 infected patients used CHM (Yang, Islam, Wang, Li, & Chen, 2020). The number and overall quality of trials investigating CHM for any coronavirus type are generally low. Published pre-clinical and cohort studies suggest CHM could be a promising therapy

for prevention and adjuvant treatment, but rigorous investigation is needed to assess efficacy and safety. Du et al report that among 214 confirmed COVID-19 cases, 90% improved with Qingfei Paidu Decoction, but location and details of the cohort are not adequately described (Du, Hou, Miao, Huang, & Liu, 2020). No human trials evaluating CHM impact on COVID-19 symptoms are yet published, but at least 10 are registered on ClinicalTrials.gov. Still, the observations of providers in China are influencing CHM practice around the world.

The Office of the National Administration of Traditional Chinese Medicine disseminated guidance recommending Qing Fei Pai Du Decoction as “suitable for mild, moderate and severe COVID-19 cases” (China, 2020). Outcomes from other trials suggest CHM could play an important role in a viral pandemic. A recent review of 28 traditional medicine guidelines (26 Chinese and 2 Korean) that provide treatment measures for COVID-19 (Ang et al, 2020). In China specifically, 17 provinces, 4 municipalities and 4 autonomous regions in mainland China officially issued traditional medicine-related guidelines for the prevention and treatment of COVID-19.

The content of the recommended formulas varied by region and municipality. Among the various formulas recommended between the herbal formula of Qing Fei Pai Du Tang (QFPD), which is a combination of 4 different herbal formulae with 21 herbs, was recommended by the Chinese national diagnosis and treatment guidelines in the treatment of COVID-19 regardless of disease stage or regional status. According to Wang Wei, the vice president and professor of Beijing University of Chinese Medicine, "since February 5th, 390,000 bags [of QFPD] have been distributed to designated hospitals and isolation points in Wuhan, and 500,000 compound granules [of QFPD] have been distributed to the whole province" [reference available in Chinese at <https://mp.weixin.qq.com/s/SNPWSecsuiyAwW8NI0nyaQ>]. We can expect a thorough safety evaluation within a year, but the urgency of the pandemic demands more swift action. This herbal formula was also recommended for the treatment of severe stage disease in the Korean guidelines.

CHM prescriptions are usually considered after a detailed in-person examination with a skilled CM practitioner that almost always includes physical examination of the tongue and pulse, and considers multiple factors including regionality. Unfortunately, the isolation demanded in this pandemic makes this in-person evaluation impossible. Moreover, the nature of blinded randomized controlled trials generally requires that the same intervention is administered regardless of individual or regional study participant characteristics. For these reasons, QFPD stands out as the most versatile single-intervention herbal formula to study in this context.

### Overview of Non-Clinical Studies

The main herbs of QFPD have antiviral effects via different mechanisms: 1) Direct effect on virus replication and autophagy, 2) Modulation of host pathways like TLRs, RIG, RLH, AMPK, P13K/AKT, MAPK/ERK signal pathways, 3) Promotion of the human defense system via T and B cell functions, 4) Free radical scavenging activities by enhancing SOD, CAT and GPX (Zhong, 2020).

In silico studies identified over 210 possible targets of QFPD and 50 common targets with COVID-19. These targets are associated with several key immunological pathways including T helper (Th) 17 cell differentiation, T cell, B cell, tumor necrosis factor (TNF), mitogen-activated protein kinase (MAPK), Vascular endothelial growth factor (VEGF), Hypoxia-inducible factor-1 (HIF-1) and Toll-like receptor (TLR) signalling with good affinity to ACE2 receptor (Wu et al., 2020; Xu et al., 2020; Zhao et al., 2020). Another primarily in silico study of QFPD validated the anti-inflammatory effects of glycyrrhizic acid and demonstrated its ability to attenuate IL-6 release by activated macrophages (Yang, 2020).

In studies of single herbs, Gan Cao/licorice root's active component, glycyrrhizin, was found to significantly inhibit SARS-CoV virus replication, adsorption, and penetration at high concentrations (4000mg/L) in isolates of coronavirus from hospitalized patients in Germany (Cinatl et al., 2003). The experiment compared glycyrrhizin with ribavirin, pyrazofurin, and mycophenolic acid. In a mouse model looking at lipopolysaccharide (LPS) induced rapid shock from platelet accumulation in the lung, glycyrrhizin was administered just before or at the same time as LPS. Glycyrrhizin significantly reduced the severity of rapid shock induced by LPS, and prevented death in both early and later periods (Yu et al., 2005).

### Overview of Clinical Studies

Published human trials evaluating CHM impact on COVID-19 symptoms are limited, but at least 10 are registered on ClinicalTrials.gov. Still, the observations of providers in China are influencing CHM practice around the world. The Office of the National Administration of Traditional Chinese Medicine disseminated guidance recommending Qing Fei Pai Du Decoction (QFPD) as suitable for mild, moderate and severe COVID-19 cases (China, 2020). Outcomes from other trials suggest CHM could play an important role in a viral pandemic.

#### QFPD during COVID-19

As of June 6, 2020 only a single human trial has been published (Wang, R 2020) regarding QFPD for COVID-19. It is an uncontrolled prospective study of 98 cases tracked symptoms, laboratory data and CT scan findings every three days during a 9-day course of treatment. At 3 days, over 70% of patients had normalization of lymphocyte percentage, AST, ALT, and D-Dimer ( $P < 0.01$ ). At day 6, 80% had normalization of laboratory indexes now including ESR and CRP ( $P < 0.01$ ). At day 9 90% of patients had normal labs. CT scans at day 6 demonstrated improvement in 79 of 98 patients (80.6%).

Clinical improvement, as determined by "recovery" (>95% reduction in symptom scores), "significant effect" (70-95% reduction in symptom scores), "effective" (30-70% reduction in symptoms scores), or invalid, is as follows: At day 3, 21% recovered, 29% demonstrated significant efficacy, and 34% were deemed effective for a total "efficacy rate" (as defined by symptom scores improved by >30%) of 84%. At day 6, the numbers were 31% recovered, 30% significant efficacy, 29% effective for a total efficacy rate of 90%. At day 9, 41% recovered, 27% reached significant efficacy, and 24% were effective for a total efficacy rate of 92%.

#### Adverse reactions to QFPD

While this study's methodology including lack of a control group leaves much to be desired, their report on adverse reactions is important considering the complete 196g decoction was administered daily for 9 days, which is a substantially larger dose than that used in the present clinical trial. In the course of treatment of 98 patients, 4 patients developed symptoms of nausea and vomiting, 2 patients developed symptoms of dizziness, and 1 patient developed symptoms of rash. When reported as adverse reactions per total days of treatment, the incidence of adverse reactions was 0.07%.

#### Broader review of CHM for viral epidemics:

The history of use of these herbal medications throughout numerous prior epidemics suggests that the therapy is immune supporting and therefore virus agnostic. This makes it worthwhile to review the literature of CHM on other similar recent viral epidemics:

##### 1. H1N1 Influenza

In a high-quality trial of 410 participants, CHM was an effective therapy during H1N1 pandemic. Wang et al. (2011) compared oseltamivir and CHM formula maxingshigan-yinqiaosan in hospitalized patients with uncomplicated H1N1 influenza. The oseltamivir and CHM group significantly reduced median time to fever resolution compared with control group (-47%, 95% Confidence Interval (CI) -56 to -35,  $p < 0.001$ ) and when compared with oseltamivir alone (-19%, 95% CI -34 to -0.3,  $p = 0.047$ ). COVID-19 is not an influenza, but this study successfully integrated conventional medication with Chinese herbs. There were no adverse events reported in the oseltamivir and CHM group (Wang et al., 2011).

Duan et al. (2011) published a high quality trial of 256 participants investigating Lianhuaqingwen Capsule (LHC) compared with oseltamivir for H1N1. The median duration of illness was no different between groups, but the LHC group experienced significant symptom reduction compared with the oseltamivir (Duan et al., 2011).

##### 2. SARS

The previous SARS pandemic of 2003 provides some insight on the role CHM could play in the current pandemic. In a meta-analysis of 12 trials investigating Chinese herbal treatment of SARS, there was no difference in mortality rates compared with controls (Liu, Zhang, He, & Li, 2012). The trials were assessed as having high risk for bias and no trials reported long-term follow-up (Liu et al., 2012). However, they did find three formulas (Kangfeidian No. 1, 2, 3) combined with conventional medicine improved the overall SARS symptom score (MD -5.43, 95% CI -7.17 to -3.69), reduced duration of fever (MD -2.50

days, 95% CI -4.10 to -0.90) (Zhang et al., 2003). But, Yi Qi Yang Ying recipe did not reduce the duration of fever compared with control (MD -1.13 days, 95% CI -.047 to 1.21) (L. S. Zhang et al., 2004). Four formulations improved more cases of absorption of pulmonary infiltration compared with conventional medicines alone (RR 1.95, 95% CI 1.16 to 3.26), (Liu et al., 2012) and one study did not find any difference between groups. Radiographic scores of lung infiltrate was greatly improved in three studies of Chinese herbal therapy compared with controls (Liu et al., 2012). Additionally, when Chinese herbs were combined with conventional medications, the total dosage of corticosteroids was significantly less at the end of the treatment period compared with a control in two studies (Liu et al., 2012).

Huoke granules were compared with penicillin and Xiaoer Shangfeng Zhike Tangjiang syrup in children with acute bronchitis. Huoke granules were superior to the control treatment to reduce duration of cough [mean difference (MD) -0.37 days, 95% Confidence Interval (95% CI) -0.57 to -0.05] and fever (MD -1.07 days, 95% CI -1.31 to -0.83) (Y. & Li, 2005). However, randomization quality and a conflict of interest (hospital produced the Huoke granules where study was performed) encourage caution.

Prevention is a central tenet of Chinese medicine practice (Huang Di Nei Jing Ling Shu, the Ancient Classic on Needle Therapy, The Complete Chinese Text with an Annotate English Translation, 2016; Ming, 2010). During the SARS outbreak of 2003, a cohort study of 16,437 participants in Hong Kong, hospital workers (n=1,063) took an herbal formula for two weeks and were compared with a control cohort (n=15,374) that did not take the formula. Study quality is difficult to assess as the methods do not clearly describe how the cohorts were recruited posing a significant risk of selection bias. Of those that took the CHM, none tested positive for SARS compared with 64 (0.4%) of the control cohort (Lau et al., 2005). The CHM formula used was modified Yu Ping Feng San (Jade Screen Powder) plus Sang Ju Yin (Mulberry Leaf and Chrysanthemum Drink).

In a narrative review, Luo et al. (2020) described two other single arm cohort studies (Xu, Jiang, Liu, & Zhang, 2006; L. Zhang, Chen, & Zeng, 2005) that followed hospital workers in Beijing and found staff who took CHM did not develop SARS. The first cohort of 3,561 doctors, nurses, and other staff took a modified Yu Ping Feng San (Jade Screen Powder) for <25 days (Xu et al., 2006). The second cohort of 163 medical staff directly treating SARS patients took the formula for six days. In both studies, the herbal intervention was intended to prevent SARS infections (L. Zhang et al., 2005). In both studies, there were no new cases of SARS amongst any of the staff that took CHM and study quality cannot be assessed due to publication in Chinese.

CHM is largely well tolerated and adverse events (AEs) in trials also tend to be mild when reported in these trials. In a narrative review, Jiang concluded CHM can be used in many conditions with minimum side effects (Jiang, 2005) In a cohort of 1,063 people who took CHM to prevent SARS infection, there were no serious adverse events (SAEs). Nineteen (1.8%) reported minor AEs of diarrhea, dizziness, and nausea, and nine participants stopped taking the formula altogether (Lau et al., 2005). Duan et al.'s (2011) RCT of patients with H1N1 reported 4 minor AEs in the CHM group. Another trial investigating oseltamivir and CHM for H1N1 influenza reported two events of nausea and vomiting with CHM alone, but none in the group that combine CHM and oseltamivir (Wang et al., 2011). In a meta-analysis of 12 CHM and SARS trials, only two trials reported AEs. There were no serious adverse events (SAEs) or AEs in the CHM groups (Liu et al., 2012).

In the current pandemic, Ni et al. reported a case report of a family (parents and one daughter) treated with both conventional medicine and CHM for COVID-19. Two family members failed to respond to other therapies, but did respond to Shuanghuanglian oral liquid with no AEs (Ni et al., 2020). Du et al. in their study reported 214 confirmed COVID-19 cases, 90% improved with Qing Fei Pai Du Decoction, but location and details of the cohort are not adequately described (Du, Hou, Miao, Huang, & Liu, 2020).

Herbal safety is a concern. Coghlan et al. (2015) evaluated 26 CHM patent formulas that were procured over the counter in Australia to verify ingredients, and analyze for toxicity and heavy metal contamination. Half of the samples contained pharmaceutical, plant or animal ingredients not included on the label and 92% had contamination or substitution (Coghlan et al., 2015). These concerns will be addressed through additional testing of the research product as described under mQFPD Risk in risk/benefit section below.

#### *Novel compounds identified in immune modulating mushrooms*

Some of the ingredients used in the traditional Chinese *materia medica* as well as in the U.S. and other countries include possibly immunologically supportive mushrooms such as turkey tail and reishi. Others, like agarikon (*Fomitopsis officinalis*, Fo), possess documented ethnomyco logical use for pulmonary conditions (Girometta, 2018).

Recently, these mushrooms along with many others have been studied to better characterize their biological activity. Prepared components of these fungi are widely used as dietary supplements by the lay public, including for the putative prevention and treatment of viral upper respiratory infections.

As a category, immune modulating mushrooms stimulate host defense and immunity due to their complex and varying polysaccharides. Some well-studied examples include (1,3;1,6)- $\beta$ -glucans, proteoglycans, and heteroglycans that comprise the chitin-based fungal cell wall (Meng, Liang, & Luo, 2016). These polysaccharides exert immunological activity through the activation of natural killer cells, macrophages, and neutrophils, as well as induction of innate immune cytokines and interleukins (Ruthes, Smiderle, & Iacomini, 2016). Mushrooms are also the source of other pharmacologically relevant compounds, such as proteins like Ling zhi-8 in reishi (Kino et al., 1989) and lectins in several species (Singh et al., 2014), triterpenes (Akihisa et al., 2007), phenols (Durgo et al., 2013), and sterols (Akihisa et al., 2007). While nutraceutical mushrooms generally confer broad immune activity, individual species often possess unique immunological properties. Turkey tail (*Trametes versicolor*, “Tv”) is known to enhance innate and adaptive immune responses (Ramberg, Nelson, & Sinnott, 2010). Recent clinical research involving Tv mycelium (Torkelson et al., 2012) suggests NK cell induction in women with breast cancer.

Other researchers cite antitumor effects (Lu et al., 2011), (Brown & Reetz, 2012), but this is generally considered to be a result of its underlying immunologic activity. Agarikon (*Fomitopsis officinalis*, “Fo”) is another mushroom of premier immunological importance. A polypore mushroom found in old-growth forests with an exceptionally long lifespan, and a species used for more than 2000 years in European pharmacopeia as an anti-inflammatory, Fo possesses several unique classes of compounds (such as chlorinated coumarins) which confer broad-spectrum antimicrobial and antiviral activity (Girometta, 2018; Hwang et al., 2013). Sections 1.1 details the antiviral and immunological activity observed with Agarikon.

The available data shows that immune modulating mushrooms are generally well tolerated. In the above-cited clinical study (Torkelson et al., 2012) in breast cancer patients (n=9), Tv was well tolerated for six weeks in the post-radiation treatment setting. Nine total adverse events were observed: “seven mild, one moderate, and only one grade 3 adverse event which was an anxiety attack in one participant that was likely unrelated to study medication” (page 3). Notably, the nausea and GI upset associated with previous clinical trials using Tv were not reported in this study. An expanded search of the literature allows an analysis of tolerability of different isolates, fractions, or parts of the Tv organism. In a clinical trial using a polysaccharopeptide (PSP) from Tv, one out of 8 participants in the PSP treatment arm reported increased gas and burping (Pallav et al., 2014). More details on mushroom risks and potential benefits are disclosed in the following section (Study Rationale/Risk / Benefit Assessment).

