### **Sub-studies 1a and 1b**

Once enrolled, all study participants will receive a package containing the following:

- 14 day supply of study medication (capsules containing either FoTv or mQFPD or placebo)
- Digital thermometer
- Urine pregnancy test (for women of child bearing potential)
- Written instructions on proper usage of study medication
- Paper study daily diary, to include daily medication diary, symptom scores, and temperature/BP measurement data
- A blood pressure cuff or glucometer will be provided to study subjects who require but do not possess one. The study participants are not responsible for lost, stolen, or damaged devices

The study package will be sent via local courier or phlebotomist who will coordinate directly with the study participant to complete delivery. Missed doses will be logged in the provided medication diary, remain unused, and be accounted for at the end of the study. Participants will continue to make every effort to maintain quarantine through vigorous hand washing and appropriate self-isolation measures. All study participants will also receive instruction to strictly avoid alcohol, cannabis, and dairy products during the study period.

During the trial period, participants will be verbally instructed on proper usage of study product, asked to take their temperature twice daily until they reach two consecutive afebrile readings. Participants with prior hypertension will also be required to take daily home measurements of their blood pressure and report any measurements of SBP <90 or >150, or DBP >90 directly to the study team. Any measurements of SBP below 80 or above 180 will be advised to seek immediate medical attention (as specified in Section 15). Participants with prior diabetes will take daily morning glucose measurements and report any blood glucose measurement >200 directly to the study team. Any measurements of blood glucose below 70 will be advised to eat a carbohydrate rich food and report to the study team, and measurements persistently below 70 will be advised to seek immediate medical attention as an immediate priority prior to reporting to the study team. Participants with congestive heart failure or using diuretics will take daily morning weight measurements using a home scale and report to the study team any weight change greater than 3 lbs (1.5 kg) during the study period.

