### 3. Concomitant Medications

All concomitant medication and concurrent therapies will be documented at

- Baseline/Screening Visit 1, Day 14 EOT visit, Day 28 Follow-up visit, and Day 58 EOS visit for sub-studies 1a and 1b; or
- Baseline, 2 weeks after vaccination # 1, 4 weeks after vaccination # 1, 2 weeks after vaccination # 2 (if applicable), 4 weeks after vaccination # 2 (if applicable), 6 months after baseline, and 12 months after baseline (for sub-study 1c)

Dose, route, unit frequency of administration, and indication for administration and dates of medication will be captured.

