#### **Exclusion Criteria**

1. Current use of investigational agents to prevent or treat COVID-19
2. Prisoners
3. Known liver disease
4. Known renal disease or acute nephritis.
5. Pregnant or breastfeeding women
6. Use of immunosuppressive medication

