#### Medicinal mushroom risk

Mushrooms have been widely consumed throughout the globe for hundreds of years. In China, the use of mushrooms extends back in time for millennia. Their overall tolerability in clinical settings has been documented by several research groups. Compared to most herbal products, safety research on mushroom products tends to be more robust, and many large-scale clinical trials of medicinal mushroom compounds have not revealed significant adverse events or drug-drug interactions (Sullivan, Smith, & Rowan, 2006). Eleven phase I, II, and III clinical trials in stomach, colorectal, esophageal, and breast cancer patients found immunomodulatory benefits with *Tv* treatment without significant adverse effects (Standish et al., 2008). The Host Defense product line (which will be providing the mushroom products to the study) launched in 2009 and has sold hundreds of millions of units of mushroom products. Consumer adverse event reports have been recorded in compliance with FDA regulations, and have been markedly low--0.003% for *Fo* and 0.002% for *Tv*.

In regard to purity of material, identity by HPTLC and microbiological testing is conducted on each batch of Host Defense finished products. Heavy metal (As, Pb, Hg, Cd) and pesticide (USP 561) testing is carried out on the raw material. The products are manufactured in full compliance with 21 CFR Part 111 Current Good Manufacturing Practice in Manufacturing, Packaging, Labeling, or Holding Operations for Dietary Supplements.

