#### FoTv risk

Host Defense *Tv* mycelium has demonstrated immunological efficacy in preclinical and clinical research settings. A review of adverse data from Host Defense indicates that the primary adverse reaction recorded with *Tv* is gastrointestinal distress- typically nausea but also diarrhea, constipation, or bloating/gas (Torkelson et al., 2012). The lack of observed cytotoxicity in the neutral red and viral yield reduction assays conducted at the BioShield Biodefense project indicates tolerability on a basic cellular level (P. Stamets, 2014, 2015). In a separate research effort with Washington State University, agarikon has been well tolerated in honeybee populations (unpublished). No clinical safety data could be identified in the literature. Host Defense product adverse event records reveal extremely few complaints - the manufacturer has received two reports of nausea since 2016, with no other reported adverse events. From 2016 to present, more than 500,000 units of Host Defense Turkey Tail and 60,000 units of Host Defense Agarikon have been consumed, thus establishing a good safety profile for human consumption.

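### Sub-studies 1a and 1c do not bar non-study use of the trial mushrooms, so placebo participants may take the active species and pull FoTv–placebo differences toward zero

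*Combined protocol and SAP*

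**What the plan says.** Section 7 (Novel compounds identified in immune modulating mushrooms) states: "Prepared components of these fungi are widely used as dietary supplements by the lay public". The same sentence says that people take them, among other reasons, against viral infections of the upper airways. Section 14 (Medicinal mushroom risk) identifies the supplier as a consumer brand: "The Host Defense product line (which will be providing the mushroom products to the study) launched in 2009". Under FoTv risk it adds that since 2016 "more than 500,000 units of Host Defense Turkey Tail and 60,000 units of Host Defense Agarikon have been consumed".

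The eligibility lists in Section 10 name no mushroom product or supplement. The nearest item, present in all three sub-studies, is "Current use of investigational agents to prevent or treat COVID-19".

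During follow-up, the only substances that 1a and 1b participants are told to avoid appear in Section 9 (Sub-studies 1a and 1b): "All study participants will also receive instruction to strictly avoid alcohol, cannabis, and dairy products during the study period". The Section 9 text for sub-study 1c contains no avoidance instruction.

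Use of other products is recorded. Section 9 (Concomitant Medications) says "All concomitant medication and concurrent therapies will be documented at" baseline and at the listed follow-up contacts. The medical history updates include medication reconciliation, 1a/1b have a Day 14 review, and the 1c diary collects other medication use. None of these names supplements. The statistical section analyses all randomized subjects and gives no rule for using these records.

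**The concern.** A placebo participant who takes a retail Trametes versicolor or Fomitopsis officinalis product receives at least part of the intervention under test. Randomization and blinding do not correct for this. The comparison becomes FoTv against a partly treated control, and the estimated difference moves toward zero.

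Two comparisons are exposed:

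- **Sub-study 1c.** This is the only sub-study said to be large enough to test efficacy. Its objectives include antibody response and vaccine side effects. Study dosing lasts four days while antibody sampling runs to six months, so a habitual user on placebo could be exposed for longer than a participant on FoTv.
- **The 1a safety comparison.** Dilution here is not conservative, because it makes the arms look alike. Section 14 names gastrointestinal distress as the main adverse reaction to Trametes versicolor, reports the FDA's concern about worsening of disease, and says the Phase 1 study is relied on to detect adverse effects.

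The plan restricts dairy but not the test species themselves, and gives no reason for the difference.

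**Working it through.** **1. The plan's own figure.** The 1c sample size is 266, 133 per arm (Section 9). It is described as sufficient for a medium effect, but no power, standard deviation or numerical effect is given, so 266 cannot be reproduced. I assume a standardized difference d = 0.5 for a medium effect, two-sided alpha 0.05 (Statistical Methods), 1:1 allocation and a normal approximation:

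power = Φ(d × √(n/2) − 1.96)

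For n = 133 per arm, √(133/2) = 8.155. With d = 0.5, power = Φ(4.077 − 1.96) = Φ(2.117) = 98.3%.

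**2. Dilution.** Let c be the share of placebo participants using a non-study product, and f the fraction of the full effect that such use delivers. The placebo mean shifts by c × f × d, so the contrast becomes d × (1 − c × f). This takes non-study use in the FoTv arm to add nothing and leaves the variance unchanged. The documents give neither c nor f; both are assumed ranges.

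| c | d, f = 1 | Power, f = 1 | d, f = 0.5 | Power, f = 0.5 |
|---|---|---|---|---|
| 0% | 0.500 | 98.3% | 0.500 | 98.3% |
| 10% | 0.450 | 95.6% | 0.475 | 97.2% |
| 20% | 0.400 | 90.4% | 0.450 | 95.6% |
| 30% | 0.350 | 81.4% | 0.425 | 93.4% |

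Example: c = 30%, f = 0.5 gives 0.425 × 8.155 − 1.96 = 1.506, and Φ(1.506) = 93.4%.

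**3. If dropout comes out of the 266.** Section 9 and Section 10 give 266 as the 1c total. The sub-study 1c paragraph of the sample size justification adds 53 for dropout (266 + 53 = 319). If 266 is the enrolled total and 20% drop out, about 106 per arm remain (266 × 0.8 / 2 = 106.4). Full-effect drop-in of 0%, 10%, 20% and 30% then gives power of 95.3%, 90.6%, 83.0% and 72.2%.

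**4. If the true effect is smaller.** With 133 per arm, the effect detectable at 80% power is (1.960 + 0.842) × √(2/133) = 0.344. At that effect, full-effect drop-in of 10% gives Φ(2.802 × 0.9 − 1.96) = 71.3%, and 20% gives Φ(2.802 × 0.8 − 1.96) = 61.1%.

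**5. Bias.** The relative shrinkage of the estimate is c × f whatever the sample size: 10% to 30% over the range above at full effect, and 5% to 15% at half effect. For an adverse-event risk difference in 1a the same factor (1 − c × f) applies. The documents give no event rates from which to put a figure on it.

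**The case against.** The strongest case on the other side has five parts.

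- **The premise is broad.** The background statement concerns a category that also includes reishi, not the two-species blend. The unit figures come from one brand, do not define a unit and have no denominator. They show that the products are on sale and taken, not that 10% to 30% of a placebo arm would use them. This stands, and it is why c is only an assumption.
- **Full-effect drop-in is unlikely.** Study dosing is 24 capsules a day; at the 500 mg given for the placebo capsule that is 12 g. A retail user would need comparable exposure to both species at the right time. This stands; full effect is an upper case.
- **The investigational-agents exclusion may already apply.** FoTv is studied under an IND, so taking it against COVID-19 could be read as use of an investigational agent. The wording is ambiguous, however. It does not clearly reach a retail supplement taken for general immune support, and it addresses current use at entry rather than later use.
- **The records exist.** Use could be examined afterwards. But supplements are not asked about by name, so capture is uncertain, and no such analysis is planned.
- **1c is meant to be broad.** It recruits a general population with wider entry criteria, where an effect over usual background use is a legitimate question. That argues against an exclusion, but not against measuring use.

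A reader might also infer that every between-arm contrast in the programme is diluted. The documents do not support this. Sub-study 1b tests mQFPD, so mushroom use there is a background co-intervention, not crossover. The recruitment and completion rates in 1a and 1b are not treatment contrasts that drop-in would dilute.

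**Conclusion.** The gap is real and limited to 1a and 1c. The plan describes public use of the trial mushrooms, does not clearly prevent it at entry or during follow-up, and analyses all randomized subjects without using the records of other products. Drop-in would bias the 1c antibody and side-effect differences and the 1a safety comparison toward no difference.

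Its size is unknown. At d = 0.5 with 133 per arm, 1c power stays at 81% or above even with 30% full-effect drop-in, and at about 93% or above if non-study use has half the effect. It would be tempting to conclude that 1c becomes underpowered. That does not follow from the documents: power below 80% requires about 106 evaluable per arm (one reading of conflicting totals) with drop-in near 30%, or a true effect well below 0.5. The case for a change rests on the avoidable bias and the low cost of preventing and measuring it, not on a demonstrated loss of power.

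**What to change.** 1. In 1a, extend the existing avoidance instruction to non-study products containing Trametes versicolor or Fomitopsis officinalis. Give 1c the same instruction from baseline through its early post-vaccination samples: day 28 for a single-dose vaccine, two weeks after the second dose for a two-dose vaccine, and day 14 for a booster.
2. Ask about these products by name at baseline and at each scheduled concomitant-medication review. In 1b, ask by name about non-study Chinese herbal formulas.
3. Report use by arm, and add a sensitivity analysis of the 1c contrasts by baseline use. Baseline use precedes randomization, so the comparison within each stratum remains randomized.

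The cost is one sentence of instruction, one question and one table, a minor burden on participants, and perhaps a few habitual users who decline.

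An exclusion with a washout is not needed. The only 30-day look-back in the protocol applies to methamphetamine and cocaine in 1b, and nothing supports it as a mushroom washout. A wider category of medicinal mushrooms would be undefined. An exclusion could also cost enrolment if use is as common as modelled: 300 screened for 1c less 20% leaves 240 against 266 needed, and 90 screened for 1a less 30% leaves 63 against 66.
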